APPENDIX B: DATA ELEMENTS

NameXSocial security numberXDate of birthXGenderXEthnicityXRaceXMarital statusXHighest education levelXWorking for incomeXHeightXXXWeightXXXInpatient/Outpatient statusXXCLINICALBaselineABaselineABaselineYeing for incomeXXXWeightXXXContext of referral*XXXXXXXXXCongenital heart diseaseXXDilated cardiomyopathyXAdriamycinToxic/AlcoholicXYinalXXX DEMOGRAPHICS	Baseline A	Baseline B	6m	12m	18m	24m	DEMOGRAPHICS	Baseline A	Baseline B	6m	12m	18m	24m
Date of birthXGenderXEthnicityXRaceXMarital statusXHighest education levelXWorking for incomeXHeightXKXHeightXKXNorting for incomeXKXHeightXKXNorting for incomeXKXHeightXKXNorting for incomeXKXNorting for incomeXKXNorting for incomeXKXNorting for incomeXNorting for incomeXKXNorting for incomeXNorting for incomeX			_	•			
Date of birthXGenderXEthnicityXRaceXMarital statusXHighest education levelXWorking for incomeXHeightXKXHeightXKXNorting for incomeXKXHeightXKXNorting for incomeXKXHeightXKXNorting for incomeXKXNorting for incomeXKXNorting for incomeXKXNorting for incomeXNorting for incomeXKXNorting for incomeXNorting for incomeX	Social security number	х					
Ethnicity X Race X Marital status X Highest education level X Working for income X Height X X Height X X Blood type X Inpatient/Outpatient status X Context of referral* Time since first cardiac diagnosis Heart failure hospitalizations in last 12mos X Primary cardiac diagnosis X Cancer X Conony artery disease X Coronary artery disease X Dilated cardiomyopathy X Adriamycin X Toxic/Alcoholic X Familial X Ischemic X Myocarditis X Other X Post-partum X Viral X Viral		х					
RaceXMarital statusXXHighest education levelXXWorking for incomeXXHeightXXWeightXXXBlood typeXXInpatient/Outpatient statusXXContext of referral*XXTime since first cardiac diagnosisXXHeart failure hospitalizations in last 12mosXXCancerXXCongenital heart diseaseXCionary artery diseaseXDilated cardionyopathyXAdriamycinXToxic/AlcoholicXFamilialXMyocarditisXOtherXYiralXXiralXXXXXXXXXXXXXXXXXXXXYXXXYXXXYXXXXXXXXXXXXXXXXXXXXXXXXXXXXXXXXXXXXXX Gender	х						Gender	х					
RaceXMarital statusXXHighest education levelXXWorking for incomeXXHeightXXWeightXXXBlood typeXXXInpatient/Outpatient statusXXContext of referral*XXTime since first cardiac diagnosisXXHeart failure hospitalizations in last 12mosXXZoncerXXCongenital heart diseaseXCoronary artery diseaseXDilated cardionyopathyXAdriamycinXToxic/AlcoholicXFamilial IdiopathicXIdiopathic IschemicXMyocarditisXViralXViralX	Ethnicity	x					
Highest education levelXXWorking for incomeXXXHeightXXXXWeightXXXXXBlood typeXXXXXInpatient/Outpatient statusXXXXContext of referral*XXXXTime since first cardiac diagnosisXXXXPrimary cardiac diagnosisXXXXPrimary cardiac diagnosisXXXXConcerXXXXCongenital heart diseaseXXXXDilated cardiomyopathyXXXXAdriamycinXXXXXIdiopathicXXXXXIdiopathicXXXXXYaralXXXXXYaralXXXXXYaralXXXXXYaralXXXXXYaralXXXXXYaralXXXXXYaralXXXXXYaralXXXXXYaralXXXXXYaralXXXXXYaralXXXXXYar	-	х					
Working for incomeXXHeightXXXXWeightXXXXXBlood typeXXXXXInpatient/Outpatient statusXXXXContext of referral*XXXXTime since first cardiac diagnosisXXXXPrimary cardiac diagnosisXXXXPrimary cardiac diagnosisXXXXConcerXXXXXCongenital heart diseaseXXXXDilated cardionyopathyXXXXAdriamycinXXXXXToxic/AlcoholicXXXXFamilialXXXXMyocarditisXXXXViralXXXX	Marital status	x			х		
HeightXXWeightXXXXXBlood typeXXXXXInpatient/Outpatient statusXXXXContext of referral*XXXXClINICALBaselineBaseline6m12m18m24mTime since first cardiac diagnosisXXXXXHeart failure hospitalizations in last 12mosXXXXXPrimary cardiac diagnosisXXXXXPrimary cardiac diagnosisXXXXXCongenital heart diseaseXXXXXDilated cardiomyopathyXXXXXAdriamycinXXXXXXIdiopathicXXXXXXIdiopathicXXXXXPost-partumXXXXXViralXXXXX	Highest education level	х					
Weight Blood typeXXXXXXXInpatient/Outpatient status Context of referral*XXXXXTime since first cardiac diagnosis Heart failure hospitalizations in last 12mosXXXXTime since first cardiac diagnosis CancerXXXXPrimary cardiac diagnosis CancerXXXXCongenital heart diseaseXXXXCoronary artery diseaseXXXXDilated cardiomyopathyXXXXAdriamycinXXXXXIdiopathic IschemicXXXXXMyocarditisXXXXXViralXXXXXX	Working for income	x			х		
Blood type X X X X Inpatient/Outpatient status X X X Context of referral* Baseline Baseline Baseline B 6m 12m 18m 24m X CLINICAL Baseline B 6m 12m 18m 24m X	Height	x	Х				
Inpatient/Outpatient status Context of referral*XXCLINICALBaseline ABaseline B6m12m18m24mTime since first cardiac diagnosis Heart failure hospitalizations in last 12mosXXXXPrimary cardiac diagnosis CancerXXXXCongenital heart diseaseXXYXCongenital heart diseaseXXYYDilated cardiomyopathyXXYYAdriamycinXYYYToxic/AlcoholicXXYYFamilial Idiopathic IschemicXXYYMyocarditis OtherXXYYViralXXYYY	Weight	x	Х	х	х	х	х
Context of referral*XCLINICALBaseline ABaseline B6m12m18m24mTime since first cardiac diagnosis Heart failure hospitalizations in last 12mosXXXXPrimary cardiac diagnosis CancerXXXXCongenital heart diseaseXXXXCoronary artery diseaseXXXXDilated cardiomyopathyXXXXAdriamycinXXXXIdiopathicXXXXIschemicXXXXMyocarditisXXXXViralXXXX	Blood type	x					
CLINICALBaseline ABaseline B6m12m18m24mTime since first cardiac diagnosis Heart failure hospitalizations in last 12mosXXXXPrimary cardiac diagnosis CancerXXXXCongenital heart disease Coronary artery diseaseX	Inpatient/Outpatient status	x	Х				
CLINICALAB6m12m18m24mTime since first cardiac diagnosis Heart failure hospitalizations in last 12mosXXXXPrimary cardiac diagnosisXXXXPrimary cardiac diagnosisXXXXCancerXXXXCongenital heart diseaseXYYCoronary artery diseaseXYYDilated cardiomyopathyXYYAdriamycinXYYToxic/AlcoholicXYYFamilialXYYIdiopathicXYYIschemicXYYMyocarditisXYYViralXYY	Context of referral*	х					
CLINICALAB6m12m18m24mTime since first cardiac diagnosis Heart failure hospitalizations in last 12mosXXXXPrimary cardiac diagnosisXXXXPrimary cardiac diagnosisXXXXCancerXXXXCongenital heart diseaseXYYCoronary artery diseaseXYYDilated cardiomyopathyXYYAdriamycinXYYToxic/AlcoholicXYYFamilialXYYIdiopathicXYYIschemicXYYMyocarditisXYYViralXYY							
Heart failure hospitalizations in last 12mosXXX12mosXXXPrimary cardiac diagnosisXXCancerXXCongenital heart diseaseXXCoronary artery diseaseXXDilated cardiomyopathyXXAdriamycinXXToxic/AlcoholicXXFamilialXXIdiopathicXXIschemicXXOtherXXPost-partumXXViralXX	CLINICAL			6m	12m	18m	24m
12mosXXXPrimary cardiac diagnosisXCancerXCongenital heart diseaseXCoronary artery diseaseXDilated cardiomyopathyXAdriamycinXToxic/AlcoholicXFamilialXIdiopathicXIschemicXMyocarditisXOtherXPost-partumXViralX	Time since first cardiac diagnosis	Х			X		х
Primary cardiac diagnosisXCancerXCongenital heart diseaseXCoronary artery diseaseXDilated cardiomyopathyXAdriamycinXToxic/AlcoholicXFamilialXIdiopathicXIschemicXMyocarditisXOtherXPost-partumXViralX		v			v		v
CancerXCongenital heart diseaseXCoronary artery diseaseXDilated cardiomyopathyXAdriamycinXToxic/AlcoholicXFamilialXIdiopathicXIschemicXMyocarditisXOtherXPost-partumXViralX					*		X
Congenital heart diseaseXCoronary artery diseaseXDilated cardiomyopathyXAdriamycinXToxic/AlcoholicXFamilialXIdiopathicXIschemicXMyocarditisXOtherXPost-partumXViralX							
Coronary artery diseaseXDilated cardiomyopathyXAdriamycinXToxic/AlcoholicXFamilialXIdiopathicXIschemicXMyocarditisXOtherXPost-partumXViralX							
Dilated cardiomyopathyXAdriamycinXToxic/AlcoholicXFamilialXIdiopathicXIschemicXMyocarditisXOtherXPost-partumXViralX	-						
AdriamycinXToxic/AlcoholicXFamilialXIdiopathicXIschemicXMyocarditisXOtherXPost-partumXViralX							
Toxic/AlcoholicXFamilialXIdiopathicXIschemicXMyocarditisXOtherXPost-partumXViralX							
FamilialXIdiopathicXIschemicXMyocarditisXOtherXPost-partumXViralX	•						
IdiopathicXIdiopathicXIschemicXMyocarditisXOtherXPost-partumXViralX							
IschemicXMyocarditisXOtherXPost-partumXViralX							
MyocarditisXOtherXPost-partumXViralX							
Other X Post-partum X Viral X							
Post-partum X Viral X							
Viral X							
	rost-partum	► ^					
Hypertrophic X	Vinel	v					

Sarcoidosis	x					
Other	X					
Previous cardiac operations	X			х		х
None	X			X		X
CABG	X			X		x
Aortic valve repair/replacement	X			X		x
Mitral valve repair/replacement	X			X		x
Congenital card surg	X			X		x
Aneurysmectomy	x			х		х
Other	x			х		х
INTERMACS patient profile	x	х	х	х	х	х
Modifiers: A, FF, none	x	х	х	х	х	х
Current NYHA class	x	х	х	х	х	х
Prior heart transplant evaluation	x	х		х		х
Eval outcome: accept, reject, defer	x	х		х		х
Prior DT VAD evaluation	x	х		х		х
Eval outcome: accept, reject, defer	x	х		х		х
Diabetes	x	х		х		х
Home oxygen	x	х		х		х
Previous renal replacement	х	х		х		х
Any dialysis	х	х		х		х
Any ultrafiltration	X	Х		х		х
Recent intubation	х	Х		Х		Х
Recent intraaortic counterpulsation (within 6m)	x	х		х		х
Inotrope Use in last 6 months	x	x		x		x
Timing; which drugs	x	X		x		x
Length of time followed by program	x	~		~		~
Referral source	x					
Reason for referral	x					
	Baseline	Baseline				
	A	В	6m	12m	18m	24m
Advanced age	X X			X		X
Patient refuses transplant				X		X
Frailty Contraindication to immunotherapy	X X			X X		X X
Malnutrition/cachexia	x			x		x
Large body mass index	x			x		x
Musculoskeletal limitations	x			x		x
History of solid organ cancer	x			x		x
History lymphoma, leukemia	x			x		x
Major stroke	x			x		x
Other cerebrovascular disease	x			x		x
Renal dysfunction	x			x		X
Pulmonary disease	x			x		X
Severe diabetes	x			x		X
Peripheral vascular disease	x			x		X
Risk of recurrent infection	x			x		X
Pulmonary hypertension	X			X		X
Recent pulmonary embolus	X			Х		Х

	l					
Allosensitization	X			X		X
Heparin-induced thrombocytopenia	X			X		X
Current infection	X			X		X
Limited cognition/understanding	X			X		X
Limited social support	X			X		X
History of illicit drug use	X			X		X
History of alcohol abuse	X			X		X
History of smoking	X			X		X
Currently smoking	X			Х		Х
Severe depression	X			Х		Х
Other major psychiatric disorder	X			Х		Х
Repeated non-compliance	X			Х		Х
More than one prior sternotomy	X			Х		Х
Mediastinal radiation	X			Х		Х
Thoracic aortic disease	Х			Х		х
History of hepatitis	Х			Х		x
Chronic coagulopathy History of human immunodeficiency	x			x		X
virus or AIDS	X			X		X
History of GI ulcers	X			X		X
History of atrial arrhythmias History of symptomatic ventricular	X			Х		X
tachycardia or defibrillator shocks	Х			Х		х
Other co-morbidity (specify)	Х			Х		Х
	Baseline					
PHYSICAL	A	Baseline B	6m	12m	18m	24m
PHYSICAL Heart rate			6m	12m X	18m	24m X
	Α	В	6m		18m	
Heart rate	A X	B X	6m	х	18m	х
Heart rate Blood pressure	A X X	B X X	6m	x x	18m	x x
Heart rate Blood pressure Jugular venous pressure	A X X X	B X X X	6m	X X X	18m	X X X
Heart rate Blood pressure Jugular venous pressure S3 gallop	A X X X X	B X X X X X	6m	X X X X	18m	X X X X
Heart rate Blood pressure Jugular venous pressure S3 gallop S4 gallop	A X X X X X	В Х Х Х Х Х	6m	X X X X X	18m	X X X X X
Heart rate Blood pressure Jugular venous pressure S3 gallop S4 gallop Peripheral edema	A X X X X X X	В Х Х Х Х Х Х	6m	X X X X X X X	18m	X X X X X X X
Heart rate Blood pressure Jugular venous pressure S3 gallop S4 gallop Peripheral edema Ascites	A X X X X X X X X	В Х Х Х Х Х Х Х	6m	X X X X X X X	18m	x x x x x x x x
Heart rate Blood pressure Jugular venous pressure S3 gallop S4 gallop Peripheral edema Ascites Hepatomegaly	A X X X X X X X X Baseline	В Х Х Х Х Х Х Х		X X X X X X X X	18m	x x x x x x x x x
Heart rate Blood pressure Jugular venous pressure S3 gallop S4 gallop Peripheral edema Ascites	A X X X X X X X X	B X X X X X X X X Baseline	6m 6m	X X X X X X X		x x x x x x x x
Heart rate Blood pressure Jugular venous pressure S3 gallop S4 gallop Peripheral edema Ascites Hepatomegaly EKG Rate	A X X X X X X X Baseline A	B X X X X X X X Baseline B X		X X X X X X X X 12m X		X X X X X X X 24m X
Heart rate Blood pressure Jugular venous pressure S3 gallop S4 gallop Peripheral edema Ascites Hepatomegaly EKG	A X X X X X X X X Baseline A X	B X X X X X X X Baseline B		X X X X X X X X 12m		X X X X X X X X 24m
Heart rate Blood pressure Jugular venous pressure S3 gallop S4 gallop Peripheral edema Ascites Hepatomegaly EKG Rate Rhythm: atria, ventricles, pacing type	A X X X X X X X Baseline A X X	B X X X X X X X Baseline B X X		X X X X X X X X 12m X X		X X X X X X X 24m X X
Heart rate Blood pressure Jugular venous pressure S3 gallop S4 gallop Peripheral edema Ascites Hepatomegaly EKG Rate Rhythm: atria, ventricles, pacing type QRS duration	A X X X X X X X Baseline A X X X Baseline	B X X X X X X X Baseline B X X X X Baseline	6m	X X X X X X X X X X X	18m	X X X X X X X 24m X X X
Heart rate Blood pressure Jugular venous pressure S3 gallop S4 gallop Peripheral edema Ascites Hepatomegaly EKG Rate Rhythm: atria, ventricles, pacing type QRS duration ECHOCARDIOGRAPHY	A X X X X X X X X Baseline A X X X X X Baseline A	B X X X X X X X Baseline B X X X X Baseline B		X X X X X X X X X 12m X X X 12m		X X X X X X X 24m X X X 24m
Heart rate Blood pressure Jugular venous pressure S3 gallop S4 gallop Peripheral edema Ascites Hepatomegaly EKG Rate Rhythm: atria, ventricles, pacing type QRS duration ECHOCARDIOGRAPHY Date	A X X X X X X X X Baseline A X X X X X X	B X X X X X X X Baseline B X X X X Baseline B X	6m	X X X X X X X X X X X X X X X X X X X	18m	X X X X X X X X X X X X X X X X X X X
Heart rate Blood pressure Jugular venous pressure S3 gallop S4 gallop Peripheral edema Ascites Hepatomegaly EKG Rate Rhythm: atria, ventricles, pacing type QRS duration ECHOCARDIOGRAPHY Date Left ventricular (LV) ejection fraction	A X X X X X X X Baseline A X X X Baseline A X X X	B X X X X X X X Baseline B X X X X Baseline B C	6m	X X X X X X X X X X 12m X X X X	18m	X X X X X X X X X X 24m X X X X X X X X X X X X X X X X X X X
Heart rate Blood pressure Jugular venous pressure S3 gallop S4 gallop Peripheral edema Ascites Hepatomegaly EKG Rate Rhythm: atria, ventricles, pacing type QRS duration ECHOCARDIOGRAPHY Date Left ventricular (LV) ejection fraction LV end-diastolic dimension	A X X X X X X X Baseline A X X X Baseline A X X X X X X X X X X X X X X X X X X	B X X X X X X X X Baseline B X X X X Baseline B C	6m	X X X X X X X X X 12m X X X X X	18m	X X X X X X X X X X 24m X X X X X X X X X X X X X X X X X X X
Heart rate Blood pressure Jugular venous pressure S3 gallop S4 gallop Peripheral edema Ascites Hepatomegaly EKG Rate Rhythm: atria, ventricles, pacing type QRS duration ECHOCARDIOGRAPHY Date Left ventricular (LV) ejection fraction LV end-diastolic dimension Right ventricular (RV) Indices	A X X X X X X X X Baseline A X X X X X X X X X X X X X X X X X X	B X X X X X X X X Baseline B X X X X Baseline B (((6m	X X X X X X X X X X X X X X X X X X X	18m	X X X X X X X X X X X X X X X X X X X
Heart rate Blood pressure Jugular venous pressure S3 gallop S4 gallop Peripheral edema Ascites Hepatomegaly EKG Rate Rhythm: atria, ventricles, pacing type QRS duration ECHOCARDIOGRAPHY Date Left ventricular (LV) ejection fraction LV end-diastolic dimension Right ventricular (RV) Indices Qualitative RV Function	A X X X X X X X X Baseline A X X X X X X X X X X X X X X X X X X	B X X X X X X X X Baseline B X X X X Baseline B (6m	X X X X X X X X X X X X X X X X X X X	18m	X X X X X X X X X X X X X X X X X X X
Heart rate Blood pressure Jugular venous pressure S3 gallop S4 gallop Peripheral edema Ascites Hepatomegaly EKG Rate Rhythm: atria, ventricles, pacing type QRS duration ECHOCARDIOGRAPHY Date Left ventricular (LV) ejection fraction LV end-diastolic dimension Right ventricular (RV) Indices	A X X X X X X X X Baseline A X X X X X X X X X X X X X X X X X X	B X X X X X X X Baseline B X X X X Baseline B (((6m	X X X X X X X X X X X X X X X X X X X	18m	X X X X X X X X X X X X X X X X X X X

1	1					
Tricuspid annular plane excursion		(Х		(X)
Tricuspid regurgitant velocity Tricuspid regurgitation (none, mild, mod,)	(Х		(X)
sev))	(х		(X)
Mitral regurgitation (none, mild, mod,						(X)
sev)		(X		(X)
Aortic stenosis (none, mild, mod, sev) Aortic insufficiency (none, mild, mod,	,	(X		
sev))	(х		(X)
Inferior vena cava size	>	(х		(X)
Inferior vena cava respiration variation: ves, blunted, none)	(х		(X)
Ancillary indices of RV function)	(х		(X)
	Baseline	Baseline		12m* If		
RIGHT HEART CATHETERIZATION	A	Baseline	6m	avail	18m	24m
Date	х			х		
Therapies at cath: no iv, iv, iabp	x			Х		
Systolic blood pressure	x			х		
Diastolic blood pressure	x			х		
heart rate	x			х		
Right atrial pressure	x			х		
Pulmonary artery systolic pressure	x			х		
Pulmonary artery diastolic pressure	x			х		
Pulmonary capillary wedge pressure	x			X		
PA saturation	X			x		
Cardiac output	x			X		
Cardiac index	X			X		
EXERCISE TESTING	Baseline A	Baseline B	6m	12m	18m	24m
6 minute walk distance	x	X	UIII	X	10111	X
15 ft walk time (gait speed/frailty)	x	X		X		X
Cardiopulmonary exercise testing		(X		
Resting heart rate)	(х		
Peak heart rate	>	(х		
Peak oxygen uptake	>	(х		
Peak oxygen uptake % predicted)	(х		
Ventilatory efficiency (Ve/VCO2))	(Х		
Peak respiratory exchange ratio)	(х		
	Baseline	Baseline				
MEDICAL AND DEVICE THERAPIES	A	Baseline	6m	12m	18m	24m
Meds: Current/Previous/No/Unknown						
Angiotensin converting enzyme inhibitor	х	Х	X	х	X	Х
Angiotensin receptor blocker	x	X	Х	х	Х	X
Beta adrenergic blocker	x	X	Х	x	Х	Х
Aldosterone antagonist	X	X	X	X	X	X
Potassium supplement	X	X	X	X	X	X
Long acting nitrate	X	X	X	X	X	X
Hydralazine	X	Х	Х	Х	Х	Х

Phosphodiesterase inhibitor	X	X	X	X	X	X
Digoxin	X	X	X	X	X	X
Loop diuretic + daily dose	X	X	Х	X	X	X
Metolazone/thiazide and frequency	X	X	Х	X	X	X
Aspirin	X	X	Х	X	X	X
Clopidogrel	X	X	х	Х	Х	X
Coumadin	X	X	х	Х	Х	X
Other anticoagulant	X	X	Х	Х	Х	Х
Statin	X	X	х	Х	Х	Х
Allopurinol	x	X	Х	Х	Х	Х
Amiodarone	x	X	х	Х	Х	Х
Other antiarrhythmic	X	X	х	Х	Х	Х
ICD	X	X	Х	Х	Х	X
If yes, dates of any ICD shocks	X	Х	х	Х	Х	Х
Cardiac resynchronization	x	Х	х	х	х	х
If < 6 months, implant date	X	Х	Х	х	х	Х
Home oxygen	x	x	X	X	X	x
	Baseline	Baseline	Gree	12m	19.00	24m
BLOOD LABORATORIES Chemistry	A	В	6m	12m	18m	24m
Sodium	x	х		х		х
Potassium	x	X		x		x
Creatinine	x	X		x		x
Blood urea nitrogen	x	X		x		x
Total bilirubin	x	~		X		X
Direct bilirubin	x			X		x
				x		x
Aspartate aminotransferase/SGOT				~		A
Aspartate aminotransferase/SGOT	X			x		Y
Alanine aminotransferase/SGPT	x	x		X X		X X
Alanine aminotransferase/SGPT B-type natriuretic peptide (BNP)	x x	X X		x		x
Alanine aminotransferase/SGPT B-type natriuretic peptide (BNP) NT-pro-BNP	x	X X				
Alanine aminotransferase/SGPT B-type natriuretic peptide (BNP) NT-pro-BNP Metabolism	x x x			x x		x x
Alanine aminotransferase/SGPT B-type natriuretic peptide (BNP) NT-pro-BNP Metabolism Total cholesterol	x x x x			x x x		x x x
Alanine aminotransferase/SGPT B-type natriuretic peptide (BNP) NT-pro-BNP Metabolism Total cholesterol Low density lipoprotein	x x x x x			x x x x		x x x x
Alanine aminotransferase/SGPT B-type natriuretic peptide (BNP) NT-pro-BNP Metabolism Total cholesterol Low density lipoprotein High density lipoprotein	x x x x x x			x x x x x x		x x x x x x
Alanine aminotransferase/SGPT B-type natriuretic peptide (BNP) NT-pro-BNP Metabolism Total cholesterol Low density lipoprotein High density lipoprotein Triglycerides	X X X X X X X			x x x x x x x		x x x x x x x
Alanine aminotransferase/SGPT B-type natriuretic peptide (BNP) NT-pro-BNP Metabolism Total cholesterol Low density lipoprotein High density lipoprotein Triglycerides Uric acid	X X X X X X X X			x x x x x x x x		x x x x x x x x
Alanine aminotransferase/SGPT B-type natriuretic peptide (BNP) NT-pro-BNP Metabolism Total cholesterol Low density lipoprotein High density lipoprotein Triglycerides Uric acid C-reactive protein	X X X X X X X X X			x x x x x x x x x		x x x x x x x x x
Alanine aminotransferase/SGPT B-type natriuretic peptide (BNP) NT-pro-BNP Metabolism Total cholesterol Low density lipoprotein High density lipoprotein Triglycerides Uric acid C-reactive protein Pre-albumin	X X X X X X X X X X			x x x x x x x x x x		x x x x x x x x x x x
Alanine aminotransferase/SGPT B-type natriuretic peptide (BNP) NT-pro-BNP Metabolism Total cholesterol Low density lipoprotein High density lipoprotein Triglycerides Uric acid C-reactive protein Pre-albumin Albumin	X X X X X X X X X X X X			X X X X X X X X X		x x x x x x x x x x x x
Alanine aminotransferase/SGPT B-type natriuretic peptide (BNP) NT-pro-BNP Metabolism Total cholesterol Low density lipoprotein High density lipoprotein Triglycerides Uric acid C-reactive protein Pre-albumin Albumin Hematologic	x x x x x x x x x x x x x x			x x x x x x x x x x x x x		x x x x x x x x x x x x x
Alanine aminotransferase/SGPT B-type natriuretic peptide (BNP) NT-pro-BNP Metabolism Total cholesterol Low density lipoprotein High density lipoprotein Triglycerides Uric acid C-reactive protein Pre-albumin Albumin Hematologic White blood cell	X X X X X X X X X X X X X			x x x x x x x x x x x x x x		x x x x x x x x x x x x x x
Alanine aminotransferase/SGPT B-type natriuretic peptide (BNP) NT-pro-BNP Metabolism Total cholesterol Low density lipoprotein High density lipoprotein Triglycerides Uric acid C-reactive protein Pre-albumin Albumin Hematologic White blood cell % lymphocytes	x x x x x x x x x x x x x x x x x			X X X X X X X X X X X X X		X X X X X X X X X X X X X
Alanine aminotransferase/SGPT B-type natriuretic peptide (BNP) NT-pro-BNP Metabolism Total cholesterol Low density lipoprotein High density lipoprotein Triglycerides Uric acid C-reactive protein Pre-albumin Albumin Hematologic White blood cell % lymphocytes Hemoglobin	x x x x x x x x x x x x x x x x x x x			X X X X X X X X X X X X X		X X X X X X X X X X X X X
Alanine aminotransferase/SGPT B-type natriuretic peptide (BNP) NT-pro-BNP Metabolism Total cholesterol Low density lipoprotein High density lipoprotein Triglycerides Uric acid C-reactive protein Pre-albumin Albumin Hematologic White blood cell % lymphocytes Hemoglobin Hematocrit	X X X X X X X X X X X X X X X X X X X			X X X X X X X X X X X X X X X		X X X X X X X X X X X X X X X
Alanine aminotransferase/SGPT B-type natriuretic peptide (BNP) NT-pro-BNP Metabolism Total cholesterol Low density lipoprotein High density lipoprotein Triglycerides Uric acid C-reactive protein Pre-albumin Albumin Hematologic White blood cell % lymphocytes Hemoglobin	x x x x x x x x x x x x x x x x x x x			X X X X X X X X X X X X X		X X X X X X X X X X X X X

QOL/PREFERENCES	Baseline A	Baseline B	6m	12m	18m	24m
EuroQoL	х	x	x	x	х	х
Thermometer	х	х	х	х	х	х
5 functional domains	х	х	х	х	х	х
Kansas City Cardiomyopathy	v	V		v		V
Questionnaire	X	X		X		X
Patient VAD survey instrument	X	X		X		X
Missing data survey	X Baseline	X Baseline		X		X
EVENTS/OUTCOMES	Α	В	6m	12m	18m	24m
Death		Х	Х	Х	х	Х
Primary cause of death (assigned by PI)		Х	Х	Х	х	Х
Sudden death		Х	х	х	х	х
Transplant		Х	Х	Х	х	Х
Listed for Transplant		Х	Х	Х	х	Х
Listing status		Х	х	х	х	х
VAD, if yes then		х	х	х	х	х
Type of circulatory support		Х	Х	Х	х	Х
Device name		Х	х	х	х	х
Intended Support Strategy Other Cardiac Procedure/Surgery		x		х		x
(name)		Х		Х		Х
Chronic inotrope infusion		Х		Х		Х
Resuscitation (Code) Status		Х		Х		Х
Hospice		Х		Х		Х
Recovery of EF to ≥40%		Х		Х		Х
Current NYHA Functional Class		Х		Х		х
Current INTERMACS Profile		Х		Х		Х
Hospitalization, reason for admission		Х		Х		Х
Heart failure with iv diuresis or inotrope		Х		Х		Х
Neurologic event		Х		Х		Х
Major bleeding (non CNS)		Х		Х		х
Transfusion		Х		Х		Х
Psychiatric episode		Х		Х		Х
Major infection		Х		Х		Х
Localized infection		Х		Х		Х
Sepsis		Х		Х		Х
Type of Infection		Х		Х		Х
Bacterial		Х		Х		Х
Fungal		Х		Х		Х
Viral		Х		Х		Х
Protozoan		Х		Х		Х
Unknown		Х		х		х
Intervention (IV, PO, surgery, other)		Х		х		х
Cardiac tachyarrhythmia		х		х		х
Syncope cause unknown Fever treated with antibiotics cause		x		х		х
unknown		Х		х		х
Arterial non-CNS thromboembolism		Х		х		х
Venous thromboembolic event		Х		х		х

Myocardial infarction	x	x	х
Other cardiac cause (specify)	X	х	х
Non-cardiac cause (specify)	X	х	x
Elective procedure - cardiac	X	х	x
Elective procedure – noncardiac	Х	x	x
Abnormal lab values	х	х	х

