2. SPECIFIC AIMS

Aim 1: To identify prospectively a population of ambulatory patients followed on optimal medical therapy for whom chronic heart failure limits both function and survival to a range where elective implantation of left ventricular assist devices should offer meaningful benefit. *Hypothesis: It will be possible to define baseline characteristics that predict a one year mortality of* \geq 35±5% for patients on medical therapy and \leq 25±5% in patients who have had VAD.

- 1.1 Characterize ambulatory patients with advanced heart failure by baseline variables and interval change, including functional capacity, frailty, and interest in technical intervention. There will be two baseline measurements one month a part (used to predict early stability) and a repeated set at 1 year (used to predict outcome between 1 and 2 years). These outcomes will include: a). All clinical parameters required for current risk score models and prediction, b). Follow-up values and changes from baseline to 1 month and baseline to 1 year as additional variables from which to predict outcomes on medical therapy, c). Functional capacity, quality of life, and patient preferences at baseline and after time.
- 1.2 Distinguish between risk factors that predict mortality whether therapy is medical or mechanical, and those risk factors that predict outcomes with different impact depending on whether therapy is medical or VAD. This will be stratified by whether patient is eligible for transplant or not.
- 1.3 Record outcomes for ambulatory patients with advanced heart failure for comparison to VAD, to include a). Hospitalizations, VAD, transplant, survival without VAD or transplant, b). Major adverse events leading to hospitalization, including infection, neurologic or bleeding, c). Functional capacity and quality of life, d). Eligibility for transplant, e). Changes in resuscitation status and enrollment in hospice.

Aim 2: To design an integrated endpoint of survival and objective functional assessment that provides more discrimination between chronic ambulatory heart failure and current device outcomes than survival alone.

Hypothesis: It will be possible to identify a composite endpoint of survival and function that will show a 30% difference between outcomes on medical therapy and outcome with initial VAD.

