6. PROCEDURES AND ASSESSMENTS

Clinical, Demographic and Laboratory Data

It has been verified that the requested data is normally acquired in the routine care of these types of patients at the referral centers for the primary investigators. Laboratory data will be obtained from routine blood draws as clinically indicated. Peak VO2 and echocardiographic parameters will be measured once during the baseline period and once at the one-year visit as clinically indicated. In those centers selected for MedaMACS, as in most centers with high volume advanced heart disease evaluation, peak VO2 and echocardiographic assessment are routine components of regular and serial evaluation. Medications, cardiac imaging, and exercise testing will occur at the discretion of the physicians caring for each study participant. Patient therapies and testing will conform to standards of care and published clinical guidelines for heart failure management.^{18, 19} Subjects will have additional functional assessment of both endurance (6 minute walk) and frailty (gait speed) one month after consent to measure early stability. Registry data will be obtained by chart review from both the electronic medical record and paper charts. Note all dates for baseline data will be by intervals rather than calendar dates. There will be a total of six data collection time points, four with face to face clinical encounters and another two by telephone: (Figure 5).

- Baseline A at consent (face to face encounter)
- Baseline B 3-6 weeks after consent (face to face encounter)
- 6 month telephone call by study site personnel
- 12 month follow-up 10-14 months after consent (face to face encounter)
- 18 month telephone call by study site personnel
- 24 month follow-up 22-26 months after consent (face to face encounter; study close)

Patient Survey

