The patient survey instrument patient will assess quality of life, health-related stress, along with impression of and thresholds for consideration of VAD therapy. All survey responses are for research only and as such will be kept confidential and not be shared with members of the medical team. This written survey will be administered at Baseline A, Baseline B, the 12 month visit and again at the 24 month study close-out visit. Patients will receive the Kansas City Cardiomyopathy Questionnaire to determine disease specific quality of life and with the Euroqol-5D questionnaire including the thermometer. There will also be a brief instrument on health-related stress identical to

the tool being used in INTERMACS. The quality of life instruments will be completed independently by the patients in a single session.

After quality of life instruments have been completed, study coordinators will read a description of a VAD and provide a simple picture. The description of a VAD will include information on implantation, anticipated benefits and potential risks. The surveys will only be administered at face-to-face visits to allow a study nurse to assist with the VAD portion of the instrument. Patients will complete the VAD portion of the survey after receiving this standard information and a study nurse will be present to answer any queries about the VAD items. Similar VAD survey items were administered in the screening pilot with excellent response rates.¹⁷ Any patient who fails to complete a survey will have a missing data form filled outlining why the self-reported instruments were not completed. In all, there are 40 questions for the patients to answer in a written format, which should take approximately 35-40 minutes for most subjects. Original copies of the written survey instruments will be kept on site by study investigators and the data will be entered electronically by the coordinators or their data assistants on site (Appendix A).

Follow-up Telephone Contact at 6 and 18 Months

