A final face to face encounter at 24 months (between 22-26 months) will be completed and the study will end at that point. Routine clinical assessment components and other study data elements will be recorded as available from the clinical record, including results of imaging and exercise testing for measurement of peak oxygen consumption, if performed at or after the 18 month time point. The six minute walk functional test will be repeated along with 5 meter gait speed to assess frailty. Patients will be re-administered the questionnaires regarding functional status, quality of life, and preferences for VAD as at baseline. Finally, at 24 months each patient

will receive the VAD survey and questionnaire to assess quality of life and perception of VAD technology. After the two year face to face visit, study participation will end.

Data Elements

A full list of data elements to be collected along with collection times may be found in Appendix B. All data will be recorded in a web based data entry system.

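### Charted code status is first recorded at Baseline B, so Aim 1.3e cannot capture changes in the first 3-6 weeks after consent; a smaller mismatch concerns 24-month peak oxygen uptake

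*Combined protocol and SAP*

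**What the plan says.** **Code status.** Section 2, Aim 1.3, item e, lists "Changes in resuscitation status and enrollment in hospice" among the outcomes to be recorded. It does not say from which visit a change is counted. In the Events/Outcomes block of Appendix B, the row "Resuscitation (Code) Status" has marks at Baseline B, 12 months and 24 months only. Section 6 sets the second visit as "Baseline B 3-6 weeks after consent (face to face encounter".

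**Preference.** Section 6, Patient Survey, states: "This written survey will be administered at Baseline A, Baseline B, the 12 month visit and again at the 24 month study close-out visit". The Appendix B row "Patient VAD survey instrument" agrees. Item 10 of the VAD survey (Appendix A, Part III) asks the patient to circle unwanted life-sustaining therapies, with chest compressions first on the list. Section 6, Follow-up Telephone Contact, adds a subset of preference questions, including resuscitation, at 6 and 18 months.

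**Peak oxygen uptake.** Section 6, End of study at 24 months, says elements are recorded as available from the clinical record, including "imaging and exercise testing for measurement of peak oxygen consumption, if performed at or after the 18 month time point". Section 6, Clinical, Demographic and Laboratory Data, names only a baseline and a one-year measurement. In Appendix B the rows under "Cardiopulmonary exercise testing" carry no 24-month mark.

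**The concern.** Most Events/Outcomes rows describe things that happen after entry, such as death or transplant, and a blank at Baseline A suits them. Code status is different: a patient may already have a limitation in the chart at consent. Without a reading there, a patient limited at consent and a patient limited two weeks later look the same in the charted data at Baseline B. The second is a change of the kind Aim 1.3e wants, and it would be counted as no change. Patients who do not reach Baseline B have no charted starting value, so they fall out of any change analysis; those among them who died early may be the ones in whom code status matters most. Section 5 allows recruitment during an admission or at the first outpatient visit after it, so the unobserved weeks may follow closely on a hospital stay.

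For peak oxygen uptake the stake is smaller. A result obtained in routine care from month 18 is to be recorded under one part of Section 6 but has no place in the data list.

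**Working it through.** The plan gives no figure to reproduce on this point. The check sets Appendix B rows side by side and compares them with the text. A dash means no mark.

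| Appendix B row (block) | A | B | 6m | 12m | 18m | 24m |
|---|---|---|---|---|---|---|
| Code status (Events/Outcomes) | - | X | - | X | - | X |
| NYHA class (Events/Outcomes) | - | X | - | X | - | X |
| INTERMACS profile (Events/Outcomes) | - | X | - | X | - | X |
| NYHA class (Clinical) | X | X | X | X | X | X |
| INTERMACS profile (Clinical) | X | X | X | X | X | X |
| Death (Events/Outcomes) | - | X | X | X | X | X |
| Patient VAD survey | X | X | - | X | - | X |
| 6-minute walk | X | X | - | X | - | X |
| Cardiopulmonary exercise (7 rows) | one baseline mark | | - | X | - | - |
| Echocardiography (legible rows) | one baseline mark | | - | X | - | (X) |

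1. Charted code status is marked at 3 of 6 time points. Change from Baseline B to 12 and 24 months is measurable; change from consent to Baseline B is not.
2. NYHA class and INTERMACS profile are also states, not events. They too are blank at Baseline A in Events/Outcomes, but each has a second row in the Clinical block that supplies a Baseline A value. Code status has no second row. The physician questionnaire given at Baseline A (Appendix A, Part I) does not ask for it either.
3. Survey item 10 gives a Baseline A reading of what the patient wants. It is not the charted order, and Section 6 says survey answers are not shared with the medical team, so the two can differ.
4. The telephone contacts ask about resuscitation preference at 6 and 18 months. Appendix B marks neither code status nor the VAD survey at those times, so the answers have no listed field.
5. Of the 7 cardiopulmonary exercise rows, 0 have a 24-month mark. The table text is damaged in extraction, but all seven rows show the same pattern, and the 6-minute walk row in the same table keeps its 24-month mark. The echocardiography rows keep a bracketed mark at 24 months, so the table has a notation for it. Right heart catheterization rows also stop at 12 months, so the echocardiography pattern does not prove that the exercise blank is accidental.
6. Within Section 6, the statement on baseline and one-year peak oxygen uptake agrees with Appendix B; the end-of-study statement does not.

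**The case against.** The strongest reply on code status is that Baseline B is a baseline. Aim 1.1 says so: "There will be two baseline measurements one month a part (used to predict early stability". Aim 1.3e names no reference visit, so counting from Baseline B satisfies it. Preference is available at consent through item 10 and does separate patients at that point. Because death is marked at Baseline B in the same block and registry data come from chart review, a site could still enter code status for a patient who died early. Much of this stands. The aim is workable without a Baseline A reading. What remains is that the preference item is not charted status, and that a status entered at Baseline B or at death is not the status at consent.

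On peak oxygen uptake, the reply is that recording is conditional, that no aim or analysis names a 24-month value, and that the 24-month functional measure in Aims 2.2 and 3.1 is the 6-minute walk, which is marked. This stands, and leaves a matter of consistency only.

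A reader might go further in three ways that the documents do not support:
- That Aim 1.3e cannot be met, or that nothing about resuscitation is known at enrolment. Baseline B and item 10 contradict this.
- That a planned two-year analysis of peak oxygen uptake is lost. None is planned.
- That the loss can be counted. Applying 35% one-year mortality at a constant hazard to all 350 patients gives 350 x (1 - 0.65^(3/52)) = 8.6 to 350 x (1 - 0.65^(6/52)) = 17 deaths before Baseline B. But Section 8 hypothesises that rate for patients with particular baseline characteristics and expects others to do better or worse, so the range is illustrative only. The documents give no rate of clinical exercise testing after month 18, so unrecorded results cannot be counted either.

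**Conclusion.** The point holds in a limited form, and it is minor. As written, the plan cannot detect charted changes in code status in the first 3-6 weeks after consent. Nor can it give a consent-time charted value for patients who die, receive a VAD or transplant, or leave before Baseline B. Changes from Baseline B to 12 and 24 months, and stated preference from Baseline A, remain available. If Baseline B is used as the reference, early changes are missed, so the count of changes since consent can only be too low for patients whose status changed once and stayed changed. The number affected is not known from the documents.

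Two smaller inconsistencies should be reconciled: the telephone preference questions without a listed field, and the conflicting statements on 24-month peak oxygen uptake. The conclusion rests on Appendix B being the complete schedule, as Section 6 says, and on the column positions that survive in the extracted table.

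**What to change.** - Mark code status at Baseline A, entered by chart review, and state in Aim 1.3e or Section 8 that changes are counted from that value.
- Add fields to Appendix B for the resuscitation preference questions asked by telephone at 6 and 18 months, or remove those questions from Section 6. State that preference and charted code status are separate variables.
- Decide whether peak oxygen uptake from month 18 onward is to be recorded. If so, add a bracketed 24-month mark to the exercise rows, as for echocardiography, and amend the baseline and one-year statement in Section 6. If not, delete it from the end-of-study paragraph.

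The cost is one form revision with matching text edits. Code status and peak oxygen uptake come from existing clinical records and the telephone questions are already planned, so no patient visit, test or question is added.
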